## 14.2 Reportable events

For the purposes of the guidance cited above and based on the definitions described above, the following events are considered reportable events in accordance with Article 80(2) of the MDR:

- a) Any serious adverse event that has a causal relationship with the investigational product, the comparator or the investigational procedure or when such a causal relationship is reasonably possible.

- b) Any product deficiency that could have resulted in a serious adverse event if appropriate action had not been taken, intervention would not have been required, or circumstances would have been less fortunate.
- c) Any new findings in relation to any of the events mentioned in letters a) and b).

### 14.3 Assessment of causality of adverse events

Investigators will request information about AEs/SAEs/DDs each time they come into contact with a patient. All AEs/SAEs/DDs reported by the patient or study personnel will be recorded in the patient's medical record and CRD.

The researcher will evaluate the causality of each AA/AAG/DD that is recorded in the corresponding CRD.

To ensure consistency in causality assessments, researchers should apply the following general rules:

Is there a reasonable possibility of a causal relationship between the study device and an adverse event based on the facts, evidence, scientific data, and appropriate medical judgment?	
AND	A temporal relationship between the AA/AAG/DD and the device under study that indicates a possible causal relationship, when the existence of other devices, therapeutic interventions or underlying disorders do not sufficiently explain the observed event.
NO	A temporal relationship between the AA/AAG/DD and the device under study that indicates an unlikely causal relationship, or the AA/AAG can be satisfactorily explained by the existence of other devices, therapeutic interventions, or underlying disorders.

***Board 2. Causality of AEs***

The sponsor and investigators will use the following definitions to evaluate the relationship of the serious adverse event to the investigational device, comparator, or investigational procedure.

Causality categories include:

1. Unrelated: The relationship with the product, comparator or procedure can be excluded when:
  - the event is not temporally related to the use of the investigational device, or the procedures related to the application of the investigational product;
  - the serious adverse event does not follow a known response pattern to the medical device (if the response pattern is previously known) and is biologically implausible;
  - The interruption of the application of the medical device or the reduction of the activation/exposure level - when clinically feasible - and the reintroduction of its use (or the increase in the activation/exposure level) do not impact the serious adverse event;

- the event affects a place in the body or an organ that cannot be affected by the product or procedure
- the serious adverse event may be attributed to another cause (for example, an underlying or concurrent disease/clinical condition, an effect of another device, medication, treatment or other risk factors)
- the event does not depend on a false result given by the investigational device used for the diagnosis, if any;

To establish non-relationship, all of the criteria listed above may not be met at the same time, depending on the type of device/procedure and the serious adverse event:

2. Possible: The relationship with the use of the investigational device or comparator, or the relationship with the procedures, is weak but cannot be completely ruled out. Alternative causes (for example, an underlying or concurrent disease/clinical condition or/and an effect of another device, medication or treatment) are also possible. Cases where the relationship cannot be assessed, or no information has been obtained, should also be classified as possible.
3. Probable: The relationship with the use of the investigational product or comparator, or the relationship with the procedures, appears relevant and/or the event cannot be reasonably explained by another cause.
4. Causal relationship: the serious adverse event is associated with the investigational product, the comparator or with the procedures beyond a reasonable doubt when:
  - the event is a known side effect of the product category to which the product belongs or similar devices and procedures;
  - the event has a temporal relationship to the use/application or procedures of the investigational device;
  - The event affects a place in the body or an organ that:
    - o the product or procedures under investigation are applied;
    - o on which the investigational product or procedures have an effect
  - the serious adverse event follows a known response pattern to the medical device (if the response pattern is previously known);
  - Discontinuing the application of the medical device (or reducing the trigger/exposure level) and reintroducing its use (or increasing the trigger/exposure level) impact the serious adverse event (when clinically feasible);

- other possible causes have been adequately ruled out (for example, an underlying or concurrent disease/clinical condition or/and an effect of another device, medication or treatment);
- the damage to the subject is due to an error in use;
- the event depends on a false result given by the investigational device used for diagnosis where applicable;

To establish the relationship, not all of the criteria listed above may be met, depending on the type of device/procedure and the serious adverse event.

The sponsor and investigators will distinguish between serious adverse events related to the investigational product and those related to procedures (any procedure specific to the clinical investigation). An adverse event may be related to both the procedures and the device under investigation. Complications caused by concomitant non-clinical investigational treatments are considered unrelated to the clinical investigation plan. Likewise, those routine diagnostic or patient management procedures, performed independently of the clinical research plan, if they are not described by the clinical research plan, the complications caused by them are also considered unrelated.

In some particular cases, the event may not be adequately evaluated because the information is insufficient or contradictory and/or the data cannot be verified or complemented. The promoter and investigators will make every effort to define and categorize the event and avoid these situations.

Where no investigator assessment is available and/or the sponsor is unsure of the serious adverse event classification of serious adverse events, the sponsor should not exclude the relationship; the event of the relationship; the event should be classified as "possible" and notification should not be delayed.

Particular attention will be paid to the assessment of causality of unforeseen serious adverse events. Their occurrence could suggest that clinical research places participating subjects at a greater risk of harm than could be expected beforehand.

## 14.4 Security plan

### 14.4.1 Registration and collection of adverse events

During scheduled evaluation visits and for the purpose of evaluating participants (study visits, phone calls, etc.), a uniform methodology will be established for asking the patient about any AEs without suggesting an answer to the questions. Below are some examples of open questions:

*How have you been feeling since your last visit?*

*Have you experienced any new problems with your health since our last contact?*

All adverse events occurring during the clinical investigation observed by the investigator or reported by the participant, whether or not attributed to the device under investigation, will be recorded in the CRD as specified in the Clinical Research Plan.

The following information will be recorded: description, start date and end date, severity, assessment of relationship to the investigational device, other suspected drug or device, and action taken. Tracking information should be provided as necessary.

#### **14.4.2 Reporting period for adverse events**

The relationship of the AEs to the device will be evaluated by a qualified investigator or by the sponsor/manufacturer and will be followed until resolution or until the event is considered stable.

All EADs that result in a participant's withdrawal from the research or are present at the end of the study should be followed up until a satisfactory resolution occurs.

#### **14.4.3 Notification of AAGs/ EAGDs/ EAIDs**

The investigator must report any AAG/EAGD/EAIDs or laboratory problems to the sponsor immediately but no later than 3 calendar days after learning of the event; regardless of the relationship to the device.

Communication will be made by email to the address: [[contact]](mailto:[contact]). The following information must be specified in the email in order to manage the incident as quickly as possible:

- Name of participating center
- Platform Tracking Plan ID
- User ID (in case the incident is related to a specific user)
- Detailed description of the incident
- Support where the incident occurred (web platform + browser / mobile app + operating system)
- Date on which the described incident occurred

The sponsor must inform the health authorities, the Clinical Research Ethics Committee and the investigators, in accordance with Article 80(2) of the MDR, the ICH-GPC guidelines, the EU Clinical Trials Regulation and other national laws or regulatory requirements applicable in the countries in which the research takes place, of the following:

- All SAEs that have a causal relationship with the investigational product, the comparator or the procedure, or whose causal relationship is reasonably possible.
- Product deficiencies that could have led to an AAG if appropriate measures had not been taken, intervention had not occurred, or circumstances had been less fortunate.
- Any new discovery related to both situations (AAG and deficiencies).

The minimum information to be communicated includes the identification of the subject, identification of the AE, start date, reason why it is considered serious, and name of the person who initially reported the event.

Any additional information regarding previously reported unexpected AEs should also be entered into the relevant form as soon as possible.

Additionally, the information must be entered into the CRD.

#### 14.4.4 Report

The sponsor will report all adverse events that are serious and have reasonable potential causality with the investigated product or procedure, in the opinion of the investigator or the sponsor, to the relevant parties within the stipulated time frames and in accordance with local regulations.

Se utilizará el formato de la MDCG 2020-10/1 Safety reporting in clinical investigations of medical devices under the Regulation (EU) 2017/745 del Appendices 12 Clinical Investigation Summary Safety Reporting Form.

#### 14.4.5 Notification periods

The sponsor shall ensure that all relevant information on suspected serious and unexpected adverse events of the product, which are fatal or life-threatening, is recorded and communicated as soon as possible to the competent authorities of all affected Member States and to the Ethics Committee.

In the case of Spain, notifications will be made to the AEMPS through the mailbox [[contact]](mailto:[contact]).

In any case, the promoter will send the information immediately and no later than 2 calendar days from the moment the promoter becomes aware of the case. This information must be completed, if possible, within the following eight days.

#### 14.4.6 Expedited notification of other relevant safety information

The sponsor must expeditiously notify all information that could modify the risk/benefit ratio of the medical device under investigation, or determine changes in its administration regimen or in the conduct of the research, for example:

- A qualitative change or increase in an expected SAE/EAGD/EAID, which is considered clinically relevant.
- Unexpected SAEs that occur after the completion of a clinical investigation and are notified by the investigator to the sponsor.
- New developments related to the conduct of the research or the development of the investigational device and that are likely to affect the safety of the subjects.
- Any recommendations from the data monitoring committee, which are relevant to the safety of the subjects.

This relevant information must be notified as soon as possible and no later than 7 calendar days after the promoter has become aware of it. Furthermore, if additional information is obtained that is relevant, it must be notified as quickly as possible.

#### 14.4.7 Monitoring of adverse events

Monitoring of AEs, especially those that could not be classified as “unrelated” due to the relationship with the product under investigation, is necessary until the reference level is reached or the subject remains stable. If a clear explanation is found, it should be entered in the CRD. If the type of AA requires the assistance of another person, the subject will be referred to the local hospital, and information about the subject's progress should also be recorded in the corresponding CRD, even if the subject has withdrawn from the clinical investigation for safety reasons. . Follow-up of AEs will continue until resolution, with confirmation if the subject remains stable, or until follow-up is no longer possible. Follow-up will be necessary for both subjects who attend the participants' clinic and those who are referred to their local hospitals for further treatment.

The safety parameter will be defined as the adverse events that occur, including those leading to withdrawal from the study.

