### 6.3 Hypothesis

The hypothesis of the study is that the implementation of a telemonitoring system in patients with heart failure will improve the quality of life and psychological well-being in patients, which will result in a decrease in symptoms of anxiety and depression, as well as a increased feeling of control over your state. Additionally, the incorporation of digital health and telemonitoring tools is expected to increase treatment adherence and improve patient clinical outcomes. On the other hand, telemonitoring is expected to be feasible and acceptable to patients, without generating significant adverse events or unwanted consequences. Ultimately, it is hypothesized that telemonitoring will allow early identification of signs of worsening in patients with heart failure, enabling timely implementation of therapeutic interventions to prevent exacerbations and optimize the clinical management of these patients.

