##### **Secondary endpoints**

- Quality of life evaluated through the "Minnesota Questionnaire for People with Heart Failure" (Change in the value of the questionnaire scale at 3 months)
- Patient-Reported Self-Care Behavior Scale Measures (EHFScB Scale) (Change in Questionnaire Scale Value at 3 Months)
- Patient adherence to treatment and medication intake (SMAQ Simplified Medication Adherence Questionnaire) (Change in the value of the questionnaire scale at 3 months)
- Death from cardiovascular (CV) causes (Total number of patients who died in 3 months)

- Mortality from any cause (Total number of patients who died in 3 months)
- Acute HF decompensation (first and recurrent) during the follow-up period (Number of total decompensations in 3 months).

An acute decompensation of HF is defined as a new episode of symptoms and signs that requires intravenous decongestive treatment or increased oral diuretics either on an outpatient basis (e.g., day or home hospitalization for HF) or at home, emergency department or requiring an unplanned hospital admission.

- Hospital readmission due to HF decompensation (Total number of hospitalizations in 3 months)
- Hospital readmission for CV causes (Total number of hospitalizations in 3 months)
- Visits to the emergency room due to HF decompensation (Total number of visits to the emergency room in 3 months)
- Visits to the emergency room for CV causes (Total number of visits to the emergency room in 3 months)
- Medical care costs (Sum of costs for medication consumption, hospitalization, emergency care and medical transportation in 3 months)

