### 14.1 Security parameters and definitions

#### 14.1.1 Adverse event (AE)

Any adverse medical event in a patient or other clinical research participant participating in a trial of a medical device, which does not have to have a causal relationship with the product investigated.

Therefore, an AE can be any unfavorable and unintentional sign, symptom or illness temporarily associated with the use of the product, whether or not considered related to the product.

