#### 14.1.4 Serious adverse event (SAE)

A Serious Adverse Event (SAE) is defined as an AE that meets one of the following conditions:

- Death during the study period (this means that the AE contributes directly or indirectly to the patient's death).
- Threat to life (defined as a subject at immediate risk of death at the time of the event).
- Requires or prolongs hospitalization.
- Causes a permanent or significant disability or disability (for example, the event disrupts the participant's normal daily activities).
- Any other significant medical event that, based on appropriate medical judgment, may endanger the subject and may require medical or surgical intervention to prevent one of the above outcomes.

All adverse events that do not meet any severity criteria should be considered as **non-serious adverse events**.

The investigator must report in the data collection notebook (CRD) all adverse events that are immediately suspected or those that are spontaneously reported by study participants, regardless of their attribution.

The AAG must be communicated to the promoter immediately by a personal telephone call.

The collection of information about AEs begins with the signing of the consent form. The subject will be questioned about any new adverse events or the evolution of previous adverse events.

Information about adverse events should be communicated as follows:

- Description
- Duration and resolution: start date and resolution date
- Maximum intensity of symptoms
- Causal relationship with study treatment
- Maximum seriousness
- Measures adopted and resolution of the event

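### The safety parameter is every adverse event whatever its cause, so it mixes effectiveness-endpoint events with harm from telemonitoring and matches the safety objective poorly

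*Combined protocol and SAP*

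**What the plan says.** Section 14.4.7 defines the safety result: "The safety parameter will be defined as the adverse events that occur, including those leading to withdrawal from the study". It neither limits this to related events nor sets endpoint events apart.

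The definitions make the total broad. Under 14.1.1 an adverse event is one "which does not have to have a causal relationship with the product investigated". Under 14.1.4 the criteria for a serious event include "Death during the study period" and "Requires or prolongs hospitalization". Under 14.4.1 all adverse events, "whether or not attributed to the device under investigation, will be recorded in the CRD".

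The secondary endpoints in 7.1.3 include "Mortality from any cause (Total number of patients who died in 3 months)" and "Hospital readmission due to HF decompensation (Total number of hospitalizations in 3 months)". They also include acute decompensations, cardiovascular readmissions, and heart failure and cardiovascular emergency visits.

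The fourth main objective in 6.1 is to identify harms associated with telemonitoring, with privacy and technical problems as its examples. The hypothesis in 6.3 expects telemonitoring to be feasible and acceptable "without generating significant adverse events or unwanted consequences".

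Section 8.1 covers subgroups, questionnaire scores, secondary endpoint events, readmissions and days in hospital. It gives no analysis or summary of adverse events, device effects or device deficiencies.

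**The concern.** The safety objective asks what telemonitoring itself brings about. The stated parameter answers a different question: how many adverse events of any kind occurred. Patients enter within 30 days of a decompensation (7.2.1), and the 3-month window was chosen because relapse is most likely then (7.1.2). Disease events are therefore likely to make up much of the total.

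Two things follow once the parameter is summarised by arm. Background disease events dilute a harm added by TM, even if TM has no effect on heart failure. If TM does reduce heart failure events, as 6.2 hopes, the reduction offsets the added harm in the same total. A statement that the 6.3 safety hypothesis was met could then rest on a figure that responds weakly, or in the wrong direction, to the harm in question.

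**Working it through.** **Overlap, from the text alone.** 14.1.1 admits events regardless of cause. 14.1.4 makes fatal events and events needing admission serious adverse events. 14.4.1 has all adverse events recorded, and 14.4.7 makes them the safety parameter. 7.1.3 lists deaths, decompensations, readmissions and emergency visits as endpoints. An emergency visit is a use of care, not an adverse event, but the medical event behind it is one. No section separates the two sets.

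**Inputs.** The plan's only computed figure is the sample of 253 (7.1.4), sized on the Minnesota questionnaire. It gives no standard deviation, so 253 cannot be reproduced, and it has no bearing on this point beyond arm size: 253/2 = 126.5, taken as 126 per arm. The plan has no figure for the safety parameter. Every event rate below is an assumption.

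**Patients with any adverse event.** Let b be the proportion of usual-care (UC) patients with an endpoint-type event, RR the TM effect on it, and d the proportion of TM patients harmed by TM. Then p(UC) = b and p(TM) = 1 - (1 - b x RR)(1 - d). For b = 0.30, RR = 0.8, d = 0.10: p(TM) = 1 - 0.76 x 0.90 = 0.316. Power is the exact probability that a two-sided Fisher test at 0.05 shows TM worse.

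| Measure | Assumptions | Power to show TM worse |
|---|---|---|
| All adverse events | b 0.30-0.50, RR 0.8, d 0.06-0.10 | 0.1-3.5% |
| All adverse events | same, RR 1.0 | 5-18% |
| Related events | d 0.06-0.10, perfect attribution, none in UC | 77-99% |
| Related events | d 0.02, 0.03, 0.04, otherwise as above | 4%, 18%, 39% |
| Related events | d 0.06-0.10, 2% background related events in each arm | 47-85% |
| Non-endpoint events | d 0.06-0.10, other adverse events in 10-40% of each arm | 6-46% |

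In the first row TM also shows no more affected patients than UC in 42-86% of trials. For related events with none in UC, the test needs at least 6 TM patients (6 against 0 gives p = 0.029; 5 against 0 gives p = 0.060), so power is P(Binomial(126, d) >= 6).

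**Event counts as a cross-check.** Assume 0.5 heart failure endpoint events and 0.5 other events per UC patient, a 20% TM reduction in the former, and 0.10 TM-caused events per TM patient.

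- All events: UC 126.5 x (0.5 + 0.5) = 126.5; TM 126.5 x (0.4 + 0.5 + 0.1) = 126.5. The ratio is 1.00 and the harm does not show.
- Non-endpoint events: UC 126.5 x 0.5 = 63.3; TM 126.5 x 0.6 = 75.9. The ratio is 1.20. The standard error of the difference is sqrt(63.3 + 75.9) = 11.8, so z = 12.65/11.8 = 1.07 and the chance of a significant excess is about 19%.

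The harm that is fully cancelled, per 100 TM patients, is 100 x (heart failure events per patient) x (1 - RR). It runs from 100 x 0.3 x 0.1 = 3 to 100 x 0.8 x 0.3 = 24 for rates of 0.3-0.8 and reductions of 10-30%.

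**The case against.** The strongest reply is that 14.4.7 only says which events make up safety. It does not collapse them into patients with any event, and no between-arm test of adverse events is planned. That stands: the Fisher test above is an illustration, and the weakness appears only when the total is compared or summarised by arm.

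A reader might infer that the trial cannot show device harm at all. The documents do not support this. Device deficiencies, device effects and serious device effects have their own definitions (14.1.2, 14.1.3, 14.1.5). Causality is assessed for each event (14.3, 14.4.1), and related serious events are notified (14.4.3). The information exists; what is missing is its place in the stated parameter and in 8.1.

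A reader might also infer that listing a death under both effectiveness and safety is an error in itself. It is not: no score adds the two, and the endpoint events have their own analysis in 8.1.

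The size of the problem is open to challenge too. Harm in 6-10% of TM patients has no source in the documents, and 14.4.8 anticipates no relevant adverse effects. The 77-99% for related events is an upper bound that drops quickly at lower harm or with background related events. The 5-18% with no TM benefit shows that dilution, not only offsetting, accounts for much of the loss.

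**Conclusion.** The point holds as a mismatch between the stated safety parameter and the objective it should serve. The overlap with the 7.1.3 endpoints follows from the definitions and needs no assumption. The loss of sensitivity does: under the assumed rates, all-event power to show TM worse is 0.1-3.5% with a 20% TM benefit and 5-18% without one. Separating the measures helps but does not make the trial well powered for safety: at most 77-99% for related events under ideal attribution, 4-39% if harm is 2-4%, and about 6-46% for non-endpoint events.

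Nothing here suggests that telemonitoring is harmful, and the primary endpoint is unaffected. The change should be made before results are seen, because a safety breakdown chosen afterwards carries less weight.

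**What to change.** In 14.4.7, with a matching entry in 8.1, report per arm the number and percentage of patients with:

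- (a) at least one adverse event judged at least possibly related to the product or a study procedure;
- (b) at least one adverse event that is not a 7.1.3 endpoint event;
- (c) at least one device deficiency, privacy issue or technical problem, since 6.1 names the last two and they need not be adverse medical events.

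Report endpoint events in the endpoint analysis, and state that any TM-caused excess of heart failure events is to be read there. Keep the all-event total beside (a) to (c). Recording and notification of serious events stay unchanged.

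The cost is a short text change and a few tables, largely from data that 14.3 and 14.4.1 already have recorded. Privacy issues may need a recording field, as none is stated.

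The limits should be stated with the results. Part (a) rests on relatedness judgements made with the arm known, and 14.3 rates as not related an event that the underlying disease explains. Part (b) has modest power. UC patients have no measuring devices (7.4), so (a) and (c) are not like-for-like between arms.
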